### **Statistical Considerations:**

The primary analysis population will include all patients registered in the study who undergo a baseline imaging study. Patients with M0 or M1 CRPC at baseline (M0 or M1 populations, respectively) will form additional analysis populations to address different questions of interest.

The primary endpoint for the study will be the occurrence of an imaging study at baseline that is positive for M1 (yes or no) among all patients enrolled with a baseline imaging study. Logistic regression analyses will be used to analyze the primary endpoint. With 1000 patients at each of the 2 possible levels of a binary variable, for a total of 2000 patients, a variable is detectable with an odds ratio of 1.312 with 80% power using a 2-sided test at alpha = 0.05, assuming an imaging study positive for M1 at baseline in 34.95% and 29.05% of patients in level 1 and level 2 of a binary variable, respectively.

Logistic regression analyses similar to those described for the primary endpoint will be used to assess most secondary endpoints. Appropriate methods accounting for the correlation of multiple studies for a patient, such as generalized estimating equations, will be used for these analyses. Cox regression analyses incorporating information on the time to occurrence of a positive imaging study will be performed to supplement these analyses.

In this study, the collection of AEs will be limited to SAEs in those patients who have received Provenge. These events will be summarized and listed by the Medical Dictionary for Regulatory Activities (MedDRA) preferred term within each system organ class.

No formal interim analysis is planned for this study.

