### **8.2 General Considerations**

#### **8.2.1 Analysis Populations**

The all-enrolled population will include all patients registered in the study. The primary analysis will be based on the primary analysis population, which will include patients in the all-enrolled population who undergo a baseline imaging study. In addition, patients with M0 or M1 CRPC at baseline (M0 or M1 populations, respectively) will form separate analysis populations to address different questions of interest.

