### **8.3.3 Exploratory Endpoints**

Prostate cancer treatment practice patterns will be summarized descriptively for patients with M0 CRPC and M1 CRPC. Prostate cancer interventions prior to study entry will be summarized. Additionally, the timing and sequence of prostate cancer interventions during the study will be summarized.

The identification of biomarkers in the M0 population that are predictive of an imaging study positive for M1 will be performed using logistic regression and Cox regression, as previously described. These analyses will be performed for both the primary endpoint (a positive imaging study at baseline) and the endpoint of a positive imaging study at any post-baseline time point.

The percentage of patients with CRPC with previously undiagnosed M1 at baseline will be calculated as 100 times the number of patients in the M1 analysis population divided by the total number of patients in the study.

Logistic regression analyses will be used to determine patient characteristics in the M0 population that are predictive of a positive imaging study at baseline as detected with different imaging modalities. The differing imaging modalities include MRI, 99mTc bone scintigraphy, or F-NaF PET/CT for bone imaging; and contrast-enhanced abdominal and pelvic CT or MRI for soft tissue imaging. For each imaging modality, multivariate logistic regression modeling will be used to identify factors that are independently predictive of a positive imaging study. These analyses will be performed for both the primary endpoint (a positive imaging study at baseline) and for the endpoint of a positive imaging study at any post-baseline time point.

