Metastasis-free survival will be defined as time from the date of the baseline imaging study to the first occurrence of M1 or death due to any cause in the M0 population. Patients who are not observed to develop M1 or who do not die will be censored at the last time observed for determination of M1. Only patients who are confirmed with M0 CRPC at study entry will be included in the analysis. Cox regression analyses will be used to analyze the MFS endpoint. Univariate Cox regression analyses will be performed separately for each baseline variable of interest. A multivariate Cox regression analysis will be performed including all baseline variables of interest. Various model selection procedures will be investigated, including forward, backward, and stepwise regression to identify a model that includes explanatory factors that are independently predictive of development of M1 or death. Supplementary analyses, including time-varying covariates of ECOG performance status and laboratory parameters, will also be provided.

Overall survival will be defined as the time from diagnosis with M1 CRPC until death. Patients who do not die will be censored at the last date they were known to be alive. Analyses similar to those described for MFS will be performed in the M1 population to determine patient characteristics that can be used to predict OS. The Kaplan-Meier method will be used to quantify the survival duration from the time of diagnosis with M1 CRPC. In addition, the effect of prostate cancer interventions and their sequencing on OS will be evaluated using a Cox regression analysis with time-varying covariates.

The timing and sequence of prostate cancer interventions will be summarized descriptively for the M1 population. The time to prostate cancer interventions will be defined as the time from the date of diagnosis with M1 CRPC until initiation of the prostate cancer intervention.

Changes in serum PSA levels during treatment for M1 CRPC will be summarized descriptively for the M1 population. For treatments with sufficient patient numbers, changes in serum PSA levels over time, PSA progression, and PSA progression-free survival will be

summarized descriptively by treatment. The maximum percentage reduction in serum PSA levels will also be summarized descriptively by treatment.

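### As written, three exploratory M1 analyses in section 8.3.3 use a population fixed at baseline and so omit patients who convert to M1 during the M0 Phase

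*Combined protocol and SAP*

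**What the plan says.** Section 8.2.1 states that "patients with M0 or M1 CRPC at baseline (M0 or M1 populations, respectively) will form separate analysis populations". The Statistical Considerations part of the synopsis agrees: "Patients with M0 or M1 CRPC at baseline (M0 or M1 populations, respectively) will form additional analysis populations".

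Section 8.3.3 relies on the baseline meaning when it defines the percentage with undiagnosed M1 at baseline, which is "calculated as 100 times the number of patients in the M1 analysis population divided by the total number of patients in the study".

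The same section then assigns three analyses to the M1 population:

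- OS predictors: "Analyses similar to those described for MFS will be performed in the M1 population to determine patient characteristics".
- Interventions, with time counted from M1 diagnosis: "The timing and sequence of prostate cancer interventions will be summarized descriptively for the M1 population".
- PSA change overall: "Changes in serum PSA levels during treatment for M1 CRPC will be summarized descriptively for the M1 population".

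Other sentences in 8.3.3 name no population. These are the Kaplan-Meier estimate of OS, the Cox model of interventions and their sequencing with time-varying covariates, and the by-treatment PSA summaries, which begin "For treatments with sufficient patient numbers, changes in serum PSA levels over time, PSA progression, and PSA progression-free survival".

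The last group of objectives in section 3.3 (interventions, PSA, OS and OS predictors) is for all patients with an M1 CRPC diagnosis, with no restriction to baseline. Sections 4.0 and 7.5 move a patient with a positive scan during the M0 Phase into the M1 Phase and collect survival, interventions and PSA there.

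**The concern.** OS and time to intervention both start at M1 diagnosis, whenever it happens, and converters are followed for exactly these outcomes. A statistician who programs the three analyses from the definition in 8.2.1 would nevertheless drop every converter. The results would describe only men whose metastases were found on the baseline scan, which is narrower than the objectives.

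A second problem follows if the analyses that name no population are run on all M1 patients. The Kaplan-Meier curve and the OS-predictor models would then describe different patients, and so would the by-treatment and overall PSA summaries. The documents do not say which set those analyses use.

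**Working it through.** **Is the M1 population really fixed at baseline?** Four places in the protocol bear on this.

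1. Section 8.2.1 and the synopsis both define it by status at baseline.
2. The percentage in 8.3.3 uses the M1 population as the count of patients with M1 at baseline. Adding converters would make that percentage wrong.
3. Section 8.3.2 models positive scans after baseline within the M0 population. Converters therefore stay in the M0 population, and 8.2.1 calls the two populations separate.
4. Metastasis-free survival in 8.3.3 is restricted to patients confirmed M0 at entry and counts first M1 as an event, which is consistent with item 3.

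No text adds converters to the M1 population. The reading is consistent, so the three analyses that name it omit converters.

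**The plan's own figure.** The only sizing statement (8.1) concerns the primary endpoint. With 1000 patients per level and rates of 34.95% and 29.05%, a two-sided 0.05 test has 80.8% power, against 80% stated, and the odds ratio is 1.312. The average rate is (34.95% + 29.05%)/2 = 32.0%, which matches the anticipated baseline rate. The plan gives no figure for the OS, intervention or PSA analyses.

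**How many patients could be left out?** Inputs from 8.1 are a baseline M1 rate p = 0.32 and N = 2000, all taken as scanned. The conversion proportion c among M0 patients is an assumption, because the documents give none and M0 Phase imaging is at the investigator's discretion.

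- M1 at baseline: 0.32 × 2000 = 640
- M0 at baseline: 2000 − 640 = 1360
- Converters: k = 1360 × c
- Share of M1 diagnoses left out: k/(640 + k)

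| Assumed c | k left out | All M1 diagnoses | Share left out |
|---|---|---|---|
| 10% | 136 | 776 | 17.5% |
| 20% | 272 | 912 | 29.8% |
| 35% | 476 | 1116 | 42.7% |
| 50% | 680 | 1320 | 51.5% |
| 60% | 816 | 1456 | 56.0% |

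In general the share is c(1 − p)/(p + c(1 − p)). N does not appear, so fewer scanned patients would lower the counts but not the shares. The baseline rate does matter. For c from 10% to 60%:

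- p = 0.25 (assumed): 0.075/0.325 = 23.1% to 0.45/0.70 = 64.3%
- p = 0.40 (assumed): 0.06/0.46 = 13.0% to 0.36/0.76 = 47.4%

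**The case against.** **It may be a drafting slip.** Converters enter the M1 Phase and complete a further ACE-27, and the clocks start at M1 diagnosis, so they were probably meant to be included. Section 8.3.3 is also loose with the sister label: it models a positive baseline scan in the M0 population, where by definition nobody has one. This stands as an account of intent. It does not change what the text instructs, and no later document corrects it, because the file states that the SAP was not finalized for lack of data.

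**The restriction may be deliberate.** The OS-predictor models follow the metastasis-free survival models, which use baseline variables. Baseline values coincide with time zero only for patients found M1 at baseline, and that group had a mandatory scan. A baseline-only model is therefore coherent. The protocol does not give this reason, however, and it would not explain the intervention or PSA summaries.

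**Interventions are partly covered elsewhere.** An earlier paragraph of 8.3.3 says: "Additionally, the timing and sequence of prostate cancer interventions during the study will be summarized". It carries no baseline restriction and may include converters. It is not timed from M1 diagnosis, and it does not touch OS predictors or PSA change.

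**The size is mostly assumption.** That is fair. Only 32% and 2000 come from the protocol, and the range shows that the share could be modest or could exceed half.

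**Conclusion.** The point holds on the text and is minor. Three exploratory analyses (OS-predictor models, the intervention summary timed from M1 diagnosis and the overall PSA-change summary) name a population that excludes converters, so they cover less than their objectives. Under assumed conversion of 10% to 60%, with the anticipated 32% baseline rate and 2000 scanned patients, that is 18% to 56% of M1 diagnoses. Because the SAP was left unfinished for insufficient data, the counts illustrate the planned study and not its actual enrolment.

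A reader might infer that every M1 analysis excludes converters, including the Kaplan-Meier OS estimate. The documents do not support that: the Kaplan-Meier, intervention Cox and by-treatment PSA sentences name no population and are unclear rather than wrong. A reader might also infer that converters' data are lost or that the main results suffer. Neither follows. Converters are followed in the M1 Phase, and the primary and secondary analyses and the sample size do not use this population in the way described. Nothing here bears on the precision of OS.

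**What to change.** - Keep the baseline-M1 population for the percentage in 8.3.3 and the baseline summaries in 8.5.
- Add to 8.2.1 an ever-M1 population: M1 at baseline or during the M0 Phase, with time zero at the first positive imaging study.
- Name it in 8.3.3 for all OS analyses, the intervention summary timed from M1 diagnosis, and all PSA analyses, overall and by treatment.
- Include detection period (baseline or M0 Phase) as a covariate or stratum in the OS models.
- Take covariates from the same source in both groups, namely the visit at which M1 was diagnosed. Use study-baseline values for variables collected only then, such as testosterone and BMI.
- If a baseline-M1-only OS-predictor model is also wanted, because baseline covariates coincide with time zero there, report it as a sensitivity analysis.

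The cost is one population definition, a few named populations and a covariate rule, with no new data collection. There are two downsides. M0 Phase visits end 3 years after the last registration and M1 follow-up ends at 5 years, so a late converter may have as little as 5 − 3 = 2 years of potential follow-up, against at least 5 years for a patient with M1 at baseline. Covariates available only from study baseline will also be older at time zero for converters.

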#### **8.4 Safety Events**

In this study, the collection of AEs will be limited to SAEs and meeting the criteria defined in Section 7.6.18. Serious adverse events will be summarized and listed by the Medical Dictionary for Regulatory Activities (MedDRA) preferred term within each system organ class. Serious adverse events that occur multiple times for a patient will be counted only once per patient in incidence summary tables. A listing of SAEs at least possibly related to Provenge will be provided.

#### **8.5 Demographic and Baseline Characteristics**

Demographic information and baseline disease characteristics will be summarized. Separate summaries will be provided for the primary analysis, M0, and M1 populations.

#### **8.6 Patient Disposition**

The disposition of all patients screened and enrolled in the study will be summarized in aggregate. Reasons for screening failure and premature study discontinuation will be summarized.

#### **8.7 Concomitant Medications**

Concomitant medications will be presented in data listings.

### **9.0 REGULATORY REQUIREMENTS**

#### **9.1 Pre-Study Documentation**

Dendreon must receive the following documentation prior to initiation of the study:

- Copy of signed Protocol Signature Page.
- Copy of curriculum vitae of Principal Investigator, updated within the past 2 years.
- Copy of current medical license for the Principal Investigator.
- Copies of financial disclosure forms for all investigators.
- Copy of the IRB approval letter for the study.
- Documentation of the IRB approval of the ICF and copy of the IRB-approved ICF.
- Copy of IRB-approved patient materials.
- IRB membership list or Department of Human and Health Services Assurance Number.

## **9.2      Investigator Obligations**

The Principal Investigator will be responsible for ensuring that all clinical study site personnel conduct the study in compliance with the Declaration of Helsinki and the ICH E6 Guideline for GCP, including the archiving of essential documents. The investigator will also ensure adherence to all national, state, and local laws of the pertinent regulatory authorities, including Federal regulations/guidelines set forth in 21 Code of Federal Regulations (CFR) §11, 50, 54, 56, and 312.

The Principal Investigator will be responsible for the patient's compliance to the study protocol, and may meet periodically with the Dendreon study monitor or Dendreon designee.

All investigators must complete and return Financial Disclosure statements (including information on spouses, legal partners, or dependent children) before study initiation. Investigators must promptly update this information if any relevant changes occur in the course of the study or in the year after the study is completed (21CFR§54.4). In addition, the Principal Investigator is responsible for providing Dendreon an adequate final report shortly after study participation is complete, in accordance with 21CFR§312.64.

## **9.3      Patient Confidentiality**

Individual patient medical information obtained as a result of this study is considered confidential and disclosure to third parties other than those noted below is prohibited. Patients' individual identifying information will be kept as confidential as possible under local, state, and federal law. Medical information may be given to the patient's personal physician or to other appropriate medical personnel responsible for the patient's welfare. Data generated as a result of this study are to be available for inspection on request by the FDA, Dendreon's representative, or the IRB. Dendreon may retain in its files copies of patient medical information required for auditing of eCRFs.

Individual patient identities will not be disclosed in any report or publication related to the study, and will not be recorded on any eCRFs maintained by Dendreon.

# **10.0    PROTOCOL MANAGEMENT AND ADMINISTRATIVE CONSIDERATIONS**

## **10.1    Study Documentation**

The investigator and study staff are responsible for maintaining a comprehensive and centralized filing system containing all study-related documentation. These files must be suitable for inspection by Dendreon, representatives of Dendreon, or the FDA at any time, and should consist of the following elements:

- Patient files, containing the completed eCRFs, supporting source documentation from the medical record including laboratory data, pathology reports, and the signed ICF.

- Regulatory files, containing the protocol with all amendments and protocol signature pages, copies of all other regulatory essential documentation, and all correspondence between the study site and the IRB and sponsor.

Records are to be available for at least 2 years after study completion and the FDA is so notified.

## **10.2 Data Collection**

Data will be entered into the electronic data capture (EDC) system. Trained study personnel will be responsible for entering data on the observations, tests, and assessments specified in the protocol into the EDC system and according to the eCRF Instructions. The eCRF Instructions will also provide the study center with data entry instructions. Data entered in the EDC system will be immediately saved to a central database and changes tracked to provide an audit trail.

## **10.3 Protocol Interpretation and Compliance**

To ensure accurate interpretation and implementation of the study, the procedures and endpoints defined in the protocol will be carefully reviewed by the investigator and his or her staff prior to the time of study initiation.

## **10.4 Study Monitoring**

A representative from Dendreon may visit each study site periodically to monitor adherence to the protocol, adherence to applicable FDA regulations, and the maintenance of adequate and accurate clinical records. Electronic case report forms will be reviewed to ensure that key data are reported as specified by the protocol. The Dendreon representative will be permitted to access patients' complete medical records, laboratory data, and other source documentation as needed to appropriately monitor the study.

## **10.5 Quality Assurance**

The Dendreon Quality Assurance department may arrange to visit the investigator in order to audit the performance of the study at the study site and the study documents originating there. The audit may be conducted by a Dendreon representative or designee. The investigator will be informed of the outcome of the audit.

In addition, inspections by health authority representatives and/or the IRB may occur at any time. The investigator must inform Dendreon Clinical Affairs or designee of any such inspection immediately. Direct access to source documents and medical records will be required for audit and inspections.

## **10.6 Disclosure of Data and Publication**

The investigator or others working on the study will submit all proposed publications, papers, abstracts or other written materials related to the study, or an outline of any proposed oral presentation with respect thereto, to Dendreon at least 1 month prior to (i) submission of such written materials for publication, or (ii) any proposed oral disclosure to a third party.

Dendreon shall have the right to comment on such written material or outline; such comments shall be considered in good faith by the investigator in determining the final form of disclosure. Notwithstanding any of the above, the investigator or others working on the study may not include any confidential information in any such publication or disclosure.

## APPENDIX 1: ECOG PERFORMANCE STATUS CRITERIA

ECOG Performance Status Scale	
Grade	Description
0	Normal activity. Fully active, able to carry on all pre-disease performance without restriction.
1	Symptoms, but ambulatory. Restricted in physically strenuous activity, but ambulatory and able to carry out work of a light or sedentary nature (e.g., light housework, office work).
2	In bed <50% of the time. Ambulatory and capable of all self-care, but unable to carry out any work activities. Up and about more than 50% of waking hours.
3	In bed >50% of the time. Capable of only limited self-care, confined to bed or chair more than 50% of waking hours.
4	100% bedridden. Completely disabled. Cannot carry on any self-care. Totally confined to bed or chair.
5	Dead.

## APPENDIX 2: ADULT COMORBIDITY EVALUATION-27

Patient #	Adult Comorbidity Evaluation-27		
P121 - _____ - _____	Date: ____/____/____ Study Staff Signature		
Cogent comorbid ailment	Grade 3 Severe Decompensation	Grade 2 Moderate Decompensation	Grade 1 Mild Decompensation
Cardiovascular System			
Myocardial Infarct	 MI $\leq$ 6 months	 MI $>$ 6 months ago	 MI by ECG only, age undetermined
Angina / Coronary Artery Disease	 Unstable angina	 Chronic exertional angina  Recent ( $\leq$ 6 months) Coronary Artery Bypass Graft (CABG) or Percutaneous Transluminal Coronary Angioplasty (PTCA)  Recent ( $\leq$ 6 months) coronary stent	 ECG or stress test evidence or catheterization evidence of coronary disease without symptoms  Angina pectoris not requiring hospitalization  CABG or PTCA ( $>$ 6 mos.)  Coronary stent ( $>$ 6 mos.)
Congestive Heart Failure (CHF)	 Hospitalized for CHF within past 6 months  Ejection fraction $<$ 20%	 Hospitalized for CHF $>$ 6 months prior  CHF with dyspnea which limits activities	 CHF with dyspnea which has responded to treatment  Exertional dyspnea  Paroxysmal Nocturnal Dyspnea (PND)
Arrhythmias	 Ventricular arrhythmia $\leq$ 6 months	 Ventricular arrhythmia $>$ 6 months  Chronic atrial fibrillation or flutter  Pacemaker	 Sick Sinus Syndrome  Supraventricular tachycardia
Hypertension	 DBP $\geq$ 130 mm Hg  Severe malignant papilledema or other eye changes  Encephalopathy	 DBP 115-129 mm Hg  DBP 90-114 mm Hg while taking antihypertensive medications  Secondary cardiovascular symptoms: vertigo, epistaxis, headaches	 DBP 90-114 mm Hg while not taking antihypertensive medications  DBP $<$ 90 mm Hg while taking antihypertensive medications  Hypertension, not otherwise specified
Venous Disease	 Recent PE ( $\leq$ 6 mos.)  Use of venous filter for PE's	 DVT controlled with Coumadin or heparin  Old PE $>$ 6 months	 Old DVT no longer treated with Coumadin or Heparin
Peripheral Arterial Disease	 Bypass or amputation for gangrene or arterial insufficiency $<$ 6 months ago  Untreated thoracic or abdominal aneurysm ( $\geq$ 6 cm)	 Bypass or amputation for gangrene or arterial insufficiency $>$ 6 months ago  Chronic insufficiency	 Intermittent claudication  Untreated thoracic or abdominal aneurysm ( $<$ 6 cm)  s/p abdominal or thoracic aortic aneurysm repair
Respiratory System			
	 Marked pulmonary insufficiency  Restrictive Lung Disease or COPD with dyspnea at rest despite treatment  Chronic supplemental O 2  CO 2 retention (pCO 2 $>$ 50 torr)  Baseline pO 2 $<$ 50 torr  FEV1 ( $<$ 50%)	 Restrictive Lung Disease or COPD (chronic bronchitis, emphysema, or asthma) with dyspnea which limits activities  FEV1 (51%-65%)	 Restrictive Lung Disease or COPD (chronic bronchitis, emphysema, or asthma) with dyspnea which has responded to treatment  FEV1 (66%-80%)
Gastrointestinal System			
Hepatic	 Portal hypertension and/or esophageal bleeding $\leq$ 6 mos. (Encephalopathy, Ascites, Jaundice with Total Bilirubin $>$ 2)	 Chronic hepatitis, cirrhosis, portal hypertension with moderate symptoms "compensated hepatic failure"	 Chronic hepatitis or cirrhosis without portal hypertension  Acute hepatitis without cirrhosis  Chronic liver disease manifested on biopsy or persistently elevated bilirubin ( $>$ 3 mg/dl)
Stomach / Intestine	 Recent ulcers ( $\leq$ 6 months ago) requiring blood transfusion	 Ulcers requiring surgery or transfusion $>$ 6 months ago	 Diagnosis of ulcers treated with meds  Chronic malabsorption syndrome  Inflammatory bowel disease (IBD) on meds or h/o with complications and/or surgery
Pancreas	 Acute or chronic pancreatitis with major complications (phlegmon, abscess, or pseudocyst)	 Uncomplicated acute pancreatitis  Chronic pancreatitis with minor complications (malabsorption, impaired glucose tolerance, or GI bleeding)	 Chronic pancreatitis w/o complications

Cogent comorbid ailment	Grade 3 Severe Decompensation	Grade 2 Moderate Decompensation	Grade 1 Mild Decompensation
Renal System			
End-stage renal disease	 Creatinine > 3 mg% with multi-organ failure, shock, or sepsis  Acute dialysis	 Chronic Renal Insufficiency with creatinine > 3 mg%  Chronic dialysis	 Chronic Renal Insufficiency with creatinine 2-3 mg%.
Endocrine System (Code the comorbid ailments with the (*) in both the Endocrine system and other organ systems if applicable)			
Diabetes Mellitus	 Hospitalization ≤ 6 months for DKA  Diabetes causing end-organ failure 
 
 retinopathy
 
 neuropathy
 
 nephropathy*
 
 coronary disease*
 
 peripheral arterial disease*
 
	 IDDM without complications  Poorly controlled AODM with oral agents	 AODM controlled by oral agents only
Neurological System			
Stroke	 Acute stroke with significant neurologic deficit	 Old stroke with neurologic residual	 Stroke with no residual  Past or recent TIA
Dementia	 Severe dementia requiring full support for activities of daily living	 Moderate dementia (not completely self-sufficient, needs supervising)	 Mild dementia (can take care of self)
Paralysis	 Paraplegia or hemiplegia requiring full support for activities of daily living	 Paraplegia or hemiplegia requiring wheelchair, able to do some self care	 Paraplegia or hemiplegia, ambulatory and providing most of self care
Neuromuscular	 MS, Parkinson's, Myasthenia Gravis, or other chronic neuromuscular disorder and requiring full support for activities of daily living	 MS, Parkinson's, Myasthenia Gravis, or other chronic neuromuscular disorder, but able to do some self care	 MS, Parkinson's, Myasthenia Gravis, or other chronic neuromuscular disorder, but ambulatory and providing most of self care
Psychiatric			
	 Recent suicidal attempt  Active schizophrenia	 Depression or bipolar disorder uncontrolled  Schizophrenia controlled w/ meds	 Depression or bipolar disorder controlled w/ medication
Rheumatologic (Incl. Rheumatoid Arthritis, Systemic Lupus, Mixed Connective Tissue Disorder, Polymyositis, Rheumatic Polymyositis)			
	 Connective Tissue Disorder with secondary end-organ failure (renal, cardiac, CNS)	 Connective Tissue Disorder on steroids or immunosuppressant medications	 Connective Tissue Disorder on NSAIDS or no treatment
Immunological System (AIDS should not be considered a comorbidity for Kaposi's Sarcoma or Non-Hodgkin's Lymphoma)			
AIDS	 Fulminant AIDS w/ KS, MAI, PCP (AIDS defining illness)	 HIV+ with h/o defining illness. CD4+ < 200/ $\mu$ L	 Asymptomatic HIV+ patient.  HIV+ w/o AIDS defining illness. CD4+ > 200/ $\mu$ L
Malignancy (Excluding Cutaneous Basal Cell Ca., Cutaneous SCCA, Carcinoma in-situ, and Intraepithelial Neoplasm)			
Solid Tumor including melanoma	 Uncontrolled cancer  Newly diagnosed but not yet treated  Metastatic solid tumor	 Any controlled solid tumor without documented metastases, but initially diagnosed and treated within the last 5 years	 Any controlled solid tumor without documented metastases, but initially diagnosed and treated > 5 years ago
Leukemia and Myeloma	 Relapse  Disease out of control	 1 st remission or new dx < 1yr  Chronic suppressive therapy	 H/o leukemia or myeloma with last Rx > 1 yr prior
Lymphoma	 Relapse	 1 st remission or new dx < 1yr  Chronic suppressive therapy	 H/o lymphoma w/ last Rx > 1 yr prior
Substance Abuse (Must be accompanied by social, behavioral, or medical complications)			
Alcohol	 Delirium tremens	 Active alcohol abuse with social, behavioral, or medical complications	 H/o alcohol abuse but not presently drinking
Illicit Drugs	 Acute Withdrawal Syndrome	 Active substance abuse with social, behavioral, or medical complications	 H/o substance abuse but not presently using
Body Weight			
Obesity		 Morbid (i.e., BMI ≥ 38)	

**OVERALL COMORBIDITY SCORE (Circle one.)**      0      1      2      3      9  
 None      Mild      Moderate      Severe      Unknown

